#### 5.7 Criteria for Taking a Participant Off Protocol Therapy

Duration of therapy will depend on individual response, evidence of disease progression and tolerance. In the absence of treatment delays due to adverse event(s), treatment may continue until one of the following criteria applies:

- Disease progression – in any subject who showed first radiologic evidence of progressive disease (PD) by RECIST 1.1 (see Section 11.1.4) and is deemed clinically stable, it is at the discretion of the investigator to continue treating the subject until progression is confirmed at least 4 weeks from the date of the first radiologic evidence of PD. Further details are described below.
- Participants who have attained a confirmed complete response (CR) that have been treated for at least 27 weeks with pembrolizumab and had at least two treatments with pembrolizumab beyond the date when the initial CR was declared. Concurrent discontinuation of Eribulin mesylate is at the discretion of the investigator. Subjects who then experience radiographic disease progression may be eligible for up to one year of additional treatment with pembrolizumab via the Second Course Phase (see below) at the discretion of the investigator if no systemic cancer treatment other than Eribulin mesylate was administered since the last dose of pembrolizumab, the subject meets the safety parameters listed in the Inclusion/Exclusion criteria, and the trial is open. Subjects will resume therapy at the same dose and schedule as at the time of initial discontinuation.
- Intercurrent illness that prevents further administration of treatment
- Unacceptable adverse event(s)
- Participant demonstrates an inability or unwillingness to comply with the medication regimen and/or documentation requirements
- Participant decides to withdraw from the protocol therapy
- General or specific changes in the participant's condition render the participant unacceptable for further treatment in the judgment of the treating investigator

Participants will be removed from the protocol therapy when any of these criteria apply. The reason for removal from protocol therapy, and the date the participant was removed, must be documented in the case report form (CRF) and recorded in the clinical trials management system (OnCore). Alternative care options will be discussed with the participant.

In the event of unusual or life-threatening complications, treating investigators must immediately notify the Overall PI, [name] MPH at [contact] or [[contact]](mailto:[contact]).

### **Confirmation of Progressive Disease**

Pembrolizumab, like other immunotherapeutic agents, may produce antitumor effects by potentiating endogenous cancer-specific immune responses. The response patterns seen with such an approach may extend beyond the typical time course of image responses seen with cytotoxic agents, and can manifest as a clinical response after an initial increase in tumor burden

or even the appearance of new lesions.

For any subject who showed first radiologic evidence of progressive disease (PD) by RECIST 1.1 (see Section 11.1.4) and is deemed clinically stable, it is at the discretion of the investigator to continue treating the subject until progression is confirmed at least 4 weeks from the date of the first radiologic evidence of PD. If progression is confirmed, the subject will be discontinued from study treatment. Otherwise, the subject will continue treatment and radiographic scans. Any subject who had initial radiologic progression and is deemed clinically unstable should be discontinued from both study drugs and no subsequent scan for confirmation is required.

Further details are as below:

For purposes of PFS assessment on this trial, in addition to radiographic assessment of tumor response or progression, the investigator should into account the clinical condition/stability of subjects.

- Clinically stable is defined by the following criteria:
  - Absence of signs and symptoms (including worsening of laboratory values) indicating disease progression
  - No decline in ECOG performance status
  - Absence of rapid progression of disease
  - Absence of progressive tumor(s) at critical anatomical sites (eg, cord compression) requiring urgent alternative medical intervention

Any subject who showed first radiologic evidence of progressive disease and is deemed clinically unstable should be discontinued from both study drugs and is not required to have repeat imaging for confirmation.

For a clinically stable subject with first radiologic evidence of progressive disease (ie, unconfirmed progression of disease), it is at the discretion of the investigator to continue treating the subject with the assigned treatment per protocol until progression of disease is confirmed on a subsequent scan at least 4 weeks later. If progression is not confirmed on the subsequent scan, the subject should continue to receive study treatment and have radiographic scans performed every 6 weeks if the patient has been on study for less than 24 weeks, or every 9 weeks for patients who have been on study greater than 24 weeks to monitor disease status. If radiologic progression is confirmed by subsequent scans, then the subject will be discontinued from study treatment. Exceptions may be considered to continue treatment in the presence of clinically stable or improved condition only after consultation with the principal investigator.

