## 11. MEASUREMENT OF EFFECT

## 11.1 Antitumor Effect – Solid Tumors

Response and progression will be evaluated in this study using the new international criteria proposed by the Response Evaluation Criteria in Solid Tumors (RECIST) guideline (version 1.1) [Eur J Ca 45:228-247, 2009]. Changes in the largest diameter (unidimensional measurement) of the tumor lesions and the shortest diameter in the case of malignant lymph nodes are used in the RECIST criteria.

Pembrolizumab, like other immunotherapeutic agents, may produce antitumor effects by potentiating endogenous cancer-specific immune responses. The response patterns seen with such an approach may extend beyond the typical time course of image responses seen with cytotoxic agents, and can manifest as a clinical response after an initial increase in tumor burden or even the appearance of new lesions.

For any subject who showed first radiologic evidence of progressive disease (PD) by RECIST 1.1 (see Section 11.1) and is deemed clinically stable, it is at the discretion of the investigator to continue treating the subject until progression is confirmed at the next scheduled restaging (or with a confirmatory completed at least 4 weeks from the initial date of PD). If progression is not confirmed on the subsequent scan, the subject should continue to receive treatment and have radiographic scans performed according to the study calendar [approximately every 3 cycles (9 weeks) for the first 12 months and then every 4 cycles (12 weeks)]. If radiologic progression is confirmed, then the subject should be discontinued from all study treatment. If the treating investigator feels that the participant is clinically stable, demonstrates improved condition, or is clearly continuing to benefit from the treatment; the PI may approve the participant to continue to receive study treatment. In all participants, the date of progression will be documented as the first date progression was observed.

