#### 11.1.3.2 Evaluation of Non-Target Lesions

Complete Response (CR): Disappearance of all non-target lesions and normalization of tumor marker level. All lymph nodes must be non-pathological in size (<10 mm short axis).

Note: If tumor markers are initially above the upper normal limit, they must normalize for a patient to be considered in complete clinical response.

Non-CR/Non-PD: Persistence of one or more non-target lesion(s) and/or maintenance of tumor marker level above the normal limits.

Progressive Disease (PD): Appearance of one or more new lesions and/or *unequivocal progression* of existing non-target lesions. *Unequivocal progression* should not normally trump target lesion status. It must be representative of overall disease status change, not a single lesion increase.

Although a clear progression of “non-target” lesions only is exceptional, the opinion of the treating physician should prevail in such circumstances, and the progression status should be confirmed at a later time by the review panel (or Principal Investigator).

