#### For Participants with Measurable Disease (*i.e.*, Target Disease)

Target Lesions	Non-Target Lesions	New Lesions	Overall Response	Best Overall Response when Confirmation is Required*
CR	CR	No	CR	4 wks Confirmation**
CR	Non-CR/Non-PD	No	PR	4 wks Confirmation**
CR	Not evaluated	No	PR	
PR	Non-CR/Non-PD/not evaluated	No	PR	
SD	Non-CR/Non-PD/not evaluated	No	SD	
PD	Any	Yes or No	PD	no prior SD, PR or CR
Any	PD***	Yes or No	PD	
Any	Any	Yes	PD	

\* See RECIST 1.1 manuscript for further details on what is evidence of a new lesion.  
 \*\* Only for non-randomized trials with response as primary endpoint.  
 \*\*\* In exceptional circumstances, unequivocal progression in non-target lesions may be accepted as disease progression.

Note: Participants with a global deterioration of health status requiring discontinuation of treatment without objective evidence of disease progression at that time should be reported as “*symptomatic deterioration*.” Every effort should be made to document the objective progression even after discontinuation of treatment.

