## **13. STATISTICAL CONSIDERATIONS**

### **13.1 Study Design/Endpoints**

This is a randomized phase II open label study of eribulin mesylate +/- Pembrolizumab for patients with metastatic HR positive breast cancer treated with 0-2 line of chemotherapy. Eighty-eight patients will be randomized (1:1) to eribulin mesylate with pembrolizumab or eribulin mesylate. Patients randomized to eribulin mesylate monotherapy will have the option to receive pembrolizumab monotherapy at time of progression.

The primary endpoint is PFS, defined as the time from study randomization to disease progression per RECIST 1.1 or death due to any cause, whichever occurred first. Patients alive without disease progression are censored at the date of last disease evaluation. The primary objective is to compare PFS of patients randomized to receive eribulin mesylate in combination with pembrolizumab (Arm A) versus those randomized to receive eribulin mesylate monotherapy (Arm B).

Secondary endpoints include PFS per irRECIST criteria, ORR per RECIST 1.1 and irRECIST, DOR, CBR, OS, safety and tolerability. For the patients randomized to the eribulin monotherapy arm who elect to receive the combination after progression, we will also perform an exploratory analysis of all clinical endpoints for patients using measurements at progression on monotherapy as the baseline tumor assessment.

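### Section 5.7 ties clinical condition to PFS assessment, in conflict with the RECIST 1.1 primary endpoint, and no section says whether an unconfirmed first progression is an event

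*Combined protocol and SAP*

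**What the plan says.** Section 13.1 sets the endpoint: "The primary endpoint is PFS, defined as the time from study randomization to disease progression per RECIST 1.1 or death due to any cause". Section 1.2 gives the same definition, and Section 13.4 applies the logrank test to PFS per RECIST 1.1. None of the three has a clinical component.

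Section 5.7, under Confirmation of Progressive Disease, opens its further details with "For purposes of PFS assessment on this trial, in addition to radiographic assessment of tumor response or progression", and continues "the investigator should into account the clinical condition/stability of subjects" (the verb is missing in the source). It then lists what makes a patient clinically stable: no symptoms, signs or laboratory worsening that point to progression, no fall in ECOG status, no rapid progression, and no progressing tumour at a critical site. For a stable patient with a first radiologic progression, "it is at the discretion of the investigator to continue treating the subject until progression is confirmed".

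Section 11.1, after its own account of treatment beyond progression, says "In all participants, the date of progression will be documented as the first date progression was observed". The note to the response table in Section 11.1.3.4 says that a decline in general health that ends treatment "without objective evidence of disease progression at that time should be reported as" symptomatic deterioration, and asks that objective progression still be sought.

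The trial is open label (Sections 1.1 and 13.1). No blinded independent review is described. For progression in non-target lesions only, Section 11.1.3.2 lets the treating physician's opinion prevail, with later confirmation by a review panel or the Principal Investigator.

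**The concern.** Two parts of the protocol give different instructions on how the primary endpoint is assessed. One uses imaging and death alone. The other adds the investigator's view of the patient's condition and names PFS as the purpose. A site that applied Section 5.7 literally would be following the protocol.

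This matters because investigators know the treatment. The reason given for patience after a first progression is a delayed immune response, and that reason concerns pembrolizumab, which Arm B receives only after progression. If a first RECIST 1.1 progression in a stable patient were set aside more often in Arm A than in Arm B, Arm A's recorded PFS would lengthen without any treatment effect, and the logrank test would be biased toward Arm A.

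**Working it through.** **1. The plan's own figure.** Inputs from Section 13.2: 70 events, medians of 4.1 and 7.1 months, one-sided alpha 0.1, 1:1 allocation, and a futility look at 35 events that stops if Z < 0.

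- Hazard ratio: 4.1/7.1 = 0.577, stated as 0.58.
- Schoenfeld: power = Φ(√70/2 × |ln 0.577| − 1.282) = Φ(2.297 − 1.282) = 84.5%.
- Freedman: power = Φ(√70 × (1 − 0.577)/(1 + 0.577) − 1.282) = Φ(2.241 − 1.282) = 83.1%.
- Schoenfeld with the futility look (bivariate normal, correlation √0.5): 83.0%.
- Expected events 24 months after the start of accrual, with 5% dropout at one year: 69.9, against 70 stated.

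The stated 83% reproduces. It rests on the event count and the hazard ratio, so clarifying which scan is the event alters no design figure.

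**2. The passages side by side, by situation.**

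| Situation | Section 5.7 | Section 11 | Status as a PFS event |
|---|---|---|---|
| First RECIST 1.1 progression, later confirmed | Clinical condition weighed for PFS; treatment may continue until confirmation | Dated at first observation (11.1) | Settled if 11.1 is followed |
| First progression, patient unstable, no second scan | Both drugs stopped | Dated at first observation (11.1) | Settled |
| First progression, stable patient, not confirmed on the next scan | Called unconfirmed; treatment and scans continue | Treatment and scans continue; no statement on the event | Not stated |
| Clinical decline without RECIST 1.1 progression | Clinical condition weighed for PFS | Symptomatic deterioration (11.1.3.4) | Excluded by the definition in 13.1, but not said outright |

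In Section 5.7 the stability criteria decide only two things: whether treatment continues and whether a confirmatory scan is needed. No sentence there says how clinical condition would create, cancel or re-date an event. The third row is the one that Section 11 does not settle.

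**3. What that row means for one patient (hypothetical).** Take scans every 9 weeks, the interval in Sections 10 and 11.1. Suppose that RECIST 1.1 progression is seen at week 9, is not confirmed at week 18, and is seen again at week 27. If the first progression is the event, PFS is 9 × 7/30.44 = 2.1 months. If it is set aside, PFS is 27 × 7/30.44 = 6.2 months. The gap of 4.1 months is as long as the control median that the plan assumes. Two analysts could build different datasets from the same scans, and neither would contradict the text.

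**4. Why no overall size is given.** The size depends on how often a first progression goes unconfirmed in each arm, and how often it would then be discounted. The documents give neither rate.

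One can simulate a related situation. With a true hazard ratio of 1, a median of 4.1 months in both arms, 9-week scans, 70 events and nominal one-sided 0.10, 3,000 runs gave a type I error of 11% with no shift. With 25% of Arm A progressions dated late, it was 12% for a 4-week delay and 21% for a one-scan delay. These figures are illustration only. Both the share and the delay are assumptions. They model late dating of progression, which is zero if Section 11.1 is followed, and they do not model a first progression that is never confirmed.

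**The case against.** The strongest reply is that the 5.7 sentence is a drafting slip in a treatment section. It lacks a verb, it introduces a definition used only for treatment decisions, and Section 11 governs measurement. Section 11.1 dates progression at first observation in all participants, and Section 11.1.3.3 likewise dates an equivocal new lesion, once confirmed, at the initial scan. Clinical decline alone has its own category. Delayed response has its own secondary endpoint, PFS per irRECIST, which suggests that the primary was meant to stay strictly RECIST 1.1. The discretion after a first progression is also written for any subject on assigned treatment, not for Arm A alone.

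Most of this stands. A reader might infer that Section 5.7 lets unblinded judgement move events at will, or that type I error is inflated by a known amount. The documents support neither: Section 5.7 contains no rule for altering an event, confirmed progression goes back to its first date, and no rate is available.

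Two things survive. The sentence names PFS as its purpose, so it cannot be read as purely about treatment. And the first-date rule says which date to use once progression is accepted. It can be read as covering an unconfirmed progression, but it does not say so, and Section 5.7 labels that case unconfirmed and continues treatment.

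**Conclusion.** The conflict is real and should be corrected, because it concerns how the primary endpoint is ascertained. It is an inconsistency in the text, not a flaw in the design. The remaining exposure is (a) sites following the 5.7 sentence instead of Section 11, and (b) a first RECIST 1.1 progression not confirmed on the next scan, whose status as an event is nowhere stated.

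Bias toward Arm A would follow only if such progressions were discounted more often in that arm. The open-label setting, the absence of a described blinded review and the pembrolizumab-specific rationale make that plausible, but the documents do not show that it would happen. If Section 11.1 is applied to every first progression, confirmed or not, the shift is zero.

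**What to change.** In Section 5.7, delete the opening words that tie the sentence to PFS assessment, or limit the sentence to the treatment-continuation decisions already described there.

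In Sections 13.1 and 13.4, add a statement such as: *For primary PFS in both arms, the event is the first scan that meets RECIST 1.1 progression, or death if earlier, whether or not the progression is later confirmed and whatever the clinical condition. Symptomatic deterioration without RECIST 1.1 progression is not itself a PFS event.*

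The cost is one sentence edited in Section 5.7 and a short addition to Section 13. No new data are needed. The treatment-continuation rules, alpha, the 70 events and the stated 83% power are unchanged.

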## **5.8 Duration of Follow Up**

Participants removed from protocol therapy for unacceptable adverse event(s) will be followed until resolution or stabilization of the adverse event.

In patients who come off trial for a reason other than progressive disease, if possible during the follow-up period, scans should be performed every 9 weeks (if the patients is within 27 weeks of

initiation of study treatment) or every 12 weeks (if the patient is greater than 54 weeks from initiation of study treatment) to evaluate for disease progression.

All participants will be followed annually by phone or by medical record until death.

## **5.9 Criteria for Taking a Participant Off Study**

Participants will be removed from study when any of the following criteria apply:

- Lost to follow-up
- Withdrawal of consent for data submission
- Death

The reason for taking a participant off study, and the date the participant was removed, must be documented in the case report form (CRF).

The research team submits a completed Off Treatment/Off Study form to ODQ when a participant comes off study. This form can be found on the ODQ website or obtained from the ODQ registration staff.

## **6. DOSING DELAYS/DOSE MODIFICATIONS**

Dose delays and modifications will be made as indicated in the following section. The descriptions and grading scales found in the revised NCI Common Terminology Criteria for Adverse Events (CTCAE) version 4.0 will be utilized for dose delays and dose modifications. A copy of the CTCAE version 4.0 can be downloaded from the CTEP website [http://ctep.cancer.gov/protocolDevelopment/electronic\\_applications/ctc.htm](http://ctep.cancer.gov/protocolDevelopment/electronic_applications/ctc.htm).

Dosing interruptions are permitted in the case of medical / surgical events or logistical reasons not related to study therapy (e.g., elective surgery, unrelated medical events, patient vacation, and/or holidays). Subjects should be placed back on study therapy within 3 weeks of the scheduled interruption, unless otherwise discussed with the Sponsor. The reason for interruption should be documented in the patient's study record.

If there are dosing delays for any reason, all study assessments are to be delayed in the same fashion, such that that scans and other assessments occur in conjunction with cycles of treatment.

**Eribulin mesylate doses may be delayed and/or reduced. No re-escalation will be allowed.**  
**Pembrolizumab may be delayed as a result of toxicities but there are no dose reductions allowed.**

**For toxicities in this Section, which are attributable to pembrolizumab alone, only pembrolizumab should be held as directed. It is permissible to continue eribulin mesylate despite discontinuation of pembrolizumab in these select cases. This will be left at physician discretion.**

**For toxicities in this Section, which are attributable to eribulin mesylate alone, it is permissible to continue pembrolizumab and is left to the treating investigator's discretion. If a decision to stop indefinitely eribulin mesylate is made, it is permissible to continue pembrolizumab despite discontinuation of eribulin mesylate in these select cases. This will be left at physician discretion.**

## 6.1 Management of toxicities attributable to pembrolizumab

Adverse events (both non-serious and serious) associated with pembrolizumab exposure may represent an immunologic etiology. These adverse events may occur shortly after the first dose or several months after the last dose of treatment. Pembrolizumab must be withheld for drug-related toxicities and severe or life-threatening AEs as per Table 4 below.

**Table 4: Dose modification guidelines for Pembrolizumab for drug-related adverse events**

General instructions:				
Immune-related AEs	Toxicity grade or conditions (CTCAEv4.0)	Action taken to pembrolizumab	irAE management with corticosteroid and/or other therapies	Monitor and follow-up
Pneumonitis	Grade 2	Withhold	

Administer corticosteroids (initial dose of 1-2 mg/kg prednisone or equivalent) followed by taper

	

Monitor participants for signs and symptoms of pneumonitis

Evaluate participants with suspected pneumonitis with radiographic imaging and initiate corticosteroid treatment

Add prophylactic antibiotics for opportunistic infections

	Grade 3 or 4, or recurrent Grade 2	Permanently discontinue		
Diarrhea / Colitis	Grade 2 or 3	Withhold	

Administer corticosteroids (initial dose of 1-2 mg/kg prednisone or equivalent) followed by taper

	

Monitor participants for signs and symptoms of enterocolitis (ie, diarrhea, abdominal pain, blood or mucus in stool with or without fever) and of bowel perforation (ie, peritoneal signs and ileus).

Participants with <math>\geq</math> Grade 2 diarrhea suspecting colitis should consider GI consultation and performing endoscopy to rule out colitis.

	Grade 4	Permanently discontinue		

				
 
Participants with diarrhea/colitis should be advised to drink liberal quantities of clear fluids. If sufficient oral fluid intake is not feasible, fluid and electrolytes should be substituted via IV infusion.
 

AST / ALT elevation or Increased bilirubin	Grade 2	Continue	
 
Consider administering corticosteroids (initial dose of 0.5 - 1 mg/kg prednisone or equivalent) followed by taper
 
	
 
Monitor with liver function tests (consider weekly or more frequently until liver enzyme value returned to baseline or is stable)
 

	Grade 3 or 4	Withhold	
 
Administer corticosteroids (initial dose of 1-2 mg/kg prednisone or equivalent) followed by taper
 
	
Type 1 diabetes mellitus (T1DM) or Hyperglycemia	Newly onset T1DM or Grade 3 or 4 hyperglycemia associated with evidence of $\beta$ -cell failure	Withhold	
 
Initiate insulin replacement therapy for participants with T1DM
 
Administer anti-hyperglycemic in participants with hyperglycemia
 
	
 
Monitor participants for hyperglycemia or other signs and symptoms of diabetes.
 

Hypophysitis	Grade 2	Withhold	
 
Administer corticosteroids and initiate hormonal replacements as clinically indicated.
 
	
 
Monitor for signs and symptoms of hypophysitis (including hypopituitarism and adrenal insufficiency)
 

	Grade 3 or 4	Withhold or permanently discontinue 		
Hyperthyroidism	Grade 2	Continue	
 
Treat with non-selective beta-blockers (eg, propranolol) or thionamides as appropriate
 
	
 
Monitor for signs and symptoms of thyroid disorders.
 

	Grade 3 or 4	Withhold or permanently discontinue 		
Hypothyroidism	Grade 2-4	Continue	
 
Initiate thyroid replacement hormones (eg, levothyroxine or liothyroinine) per standard of care
 
	
 
Monitor for signs and symptoms of thyroid disorders.
 

Nephritis and Renal dysfunction	Grade 2	Withhold	
 
Administer corticosteroids (prednisone 1-2 mg/kg or equivalent) followed by taper.
 
	
 
Monitor changes of renal function
 

	Grade 3 or 4	Permanently discontinue		
Myocarditis	Grade 1 or 2	Withhold	
 
Based on severity of AE administer corticosteroids
 
	
 
Ensure adequate evaluation to confirm etiology and/or exclude other cause
 

	Grade 3 or 4	Permanently discontinue		
Infusion Reaction 	Grade 3 or 4	Permanently discontinue	
 
See Table 5
 
	
 
See Table 5
 

All other immune-related AEs	Intolerable/ persistent Grade 2	Withhold		

	Grade 3	Withhold or discontinue based on the type of event. Events that require discontinuation include and not limited to: Gullain-Barre Syndrome, encephalitis	
 
Based on type and severity of AE administer corticosteroids
 
Ensure adequate evaluation to confirm etiology and/or exclude other causes
 

	Grade 4 or recurrent Grade 3	Permanently discontinue	

1. Withhold or permanently discontinue pembrolizumab is at the discretion of the investigator or treating physician.
 
2. See Table 5 for further guidance on all grades of pembrolizumab infusion reactions.
 
NOTE: For participants with Grade 3 or 4 immune-related endocrinopathy where withhold of pembrolizumab is required, pembrolizumab may be resumed when AE resolves to <math>\leq</math> Grade 2 and is controlled with hormonal replacement therapy or achieved metabolic control (in case of T1DM).
			

